10.1 Statistical Methods

All data collected will be summarized and presented. Continuous variables will be described as the mean, median, standard deviation, and range of n observations. Categorical data will be described with contingency tables including frequency and percentage. Individual patient listings of all data will be generated and presented. Sensitivity, specificity positive predictive value and negative predictive value will be calculated using EGD as the gold standard. Comparison between readers will be measured by a Kappa statistic. Statistical tests will be performed at the University of Massachusetts Medical School. Statistical descriptions and analyses will be carried out using STATA version 13.

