4.2 Study Endpoints

Primary

Effectiveness:

For both MCC, MCC-T and EGD, rates of diagnosis of clinically relevant pathology in patients with upper abdominal pain will be assessed. Detection of D2 findings will be considered positive. Sensitivity, specificity, positive predictive value, and negative predictive values will be calculated for both MCC and EGD. In this study the “gold standard” will be the expert group’s decision regarding the presence of an abnormal finding. McNemar’s test will be used to assess for statistically significant differences between the two modalities. Sub-analyses will be performed to compare accuracies of the two modalities based on anatomic region (i.e. esophagus, stomach, duodenum) and across various lesions (i.e. ulcers, gastropathy, esophagitis, etc.).

Safety: Rate of device or procedure related adverse events during the procedures or in the follow-up period (24 hrs. post procedure).

Secondary

Examination completion: Compare rates of complete examination of the foregut by MCC or MCC-T and EGD in patients presenting with upper abdominal complaints using sets of predetermined still images

Patient Satisfaction: Assess patient satisfaction for patients undergoing MCC or MCC-T and EGD.

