10.5 Efficacy Analysis

1) Clinical success – Diagnostic yield

For both MCC-T and EGD, we will be assessing rates of diagnosis of clinically relevant pathology in patients with upper abdominal pain. Detection of D2 findings will be considered positive. Sensitivity, specificity, positive predictive value, and negative predictive values will be calculated for both MCC-T and EGD. In this study the “gold standard” will be the expert group’s decision regarding the presence of a relevant finding. McNemar’s test will be used to assess for statistically significant differences between the two modalities. Sub-analyses will be performed to compare accuracies of the two modalities based on anatomic region (i.e. esophagus, stomach, duodenum) and across various lesions (i.e. ulcers, gastropathy, esophagitis, etc.).

2) Secondary Outcomes

Technical success:

- i. We will assess the ability of the -MCC-T and the EGD to photo document the esophagus, stomach, and duodenum as described in this protocol.
- ii. We will assess the ability of the MCC-T to be released upon command in the stomach once esophageal examination is complete.

Learning curves:

When training staff to use the device, we will assess how many capsules it takes to obtain “competency.” This will be defined as being able to obtain the appropriate photo documentation as described above at a 90% success level.

Patient satisfaction

Patient responses will be analyzed on a Likert scale to determine which procedure did the patients prefer.

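### Section 10.1 scores accuracy against EGD while the synopsis, 4.2 and 10.5 score it against the expert group; under 10.1 the accuracy measures can never favour the capsule

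*Combined protocol and SAP*

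**What the plan says.** Section 10.1 (Statistical Methods) gives a general rule: "Sensitivity, specificity positive predictive value and negative predictive value will be calculated using EGD as the gold standard".

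Section 10.5 (Efficacy Analysis) says that in this study the gold standard "will be the expert group’s decision regarding the presence of a relevant finding". The primary endpoint in the synopsis says the same. Section 4.2 also names the expert group, but its target is a "decision regarding the presence of an abnormal finding".

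All three endpoint texts want the accuracy of EGD measured too. In 10.5: "Sensitivity, specificity, positive predictive value, and negative predictive values will be calculated for both MCC-T and EGD". In 4.2: "Sensitivity, specificity, positive predictive value, and negative predictive values will be calculated for both MCC and EGD". The rule for a positive test is common to all three: "Detection of D2 findings will be considered positive". The synopsis adds that D2 means clinically relevant.

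Section 6.7 describes the expert process. Two attendings independently review both examinations, ask whether either one found a lesion likely to explain the symptoms, and grade findings D0 to D2. It gives no rule for disagreement.

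**The concern.** A reference standard settles what counts as a true or false result, and here the plan names two. The four measures in 10.1 are planned only under the primary effectiveness endpoint, so that is where the conflict falls, although 10.1 does not use the word primary.

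The choice is not neutral. If EGD is the reference, its own accuracy is fixed at 100% and the request for EGD's sensitivity and specificity has no content. The design clearly expects some findings on only one test, since 6.7 asks about either examination and then checks whether both showed the lesion. Under 10.1 the capsule cannot be credited for a patient in whom it alone was positive. If the choice stays open until the data are in, the reported comparison can turn on which sentence is followed.

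A smaller inconsistency sits alongside. Read literally, abnormal in 4.2 would make a patient with only D0 or D1 findings reference-positive although neither test could be positive, which lowers sensitivity for both.

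**Working it through.** The plan gives no expected rates, power or alpha, so there is no figure of its own to reproduce. The check is 2×2 algebra followed by an illustration.

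**Notation, per patient.** a = D2 on both tests; b = capsule only; c = EGD only; d = neither.

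**EGD as reference (10.1).**
- EGD: sensitivity (a+c)/(a+c) = 1 and specificity (b+d)/(b+d) = 1; PPV and NPV are 1 likewise.
- Capsule: sensitivity a/(a+c), specificity d/(b+d), PPV a/(a+b), NPV d/(c+d). All b patients are false positives.
- A paired test of sensitivity has discordant counts 0 v c, and one of specificity has 0 v b, each against the capsule. The capsule can at best tie.

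**Expert panel as reference (10.5), if every finding is accepted.**
- Capsule sensitivity (a+b)/(a+b+c); EGD sensitivity (a+c)/(a+b+c). Either test can come out ahead.

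**Raw D2 yield.** McNemar's test compares b with c. No reference standard enters.

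**Illustration 1: equal yields.** N = 70 is the patient number in 10.6. The counts a = 14, b = 6, c = 6 are assumed, so d = 70 − 26 = 44.

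| | EGD reference | Panel accepting all |
|---|---|---|
| Capsule sensitivity | 14/20 = 70.0% | 20/26 = 76.9% |
| EGD sensitivity | 20/20 = 100% | 20/26 = 76.9% |
| Exact McNemar, sensitivity | 0 v 6, p = 2 × 0.5⁶ = 0.031 | 6 v 6, p = 1.0 |
| Capsule specificity | 44/50 = 88.0% | 44/44 = 100% |
| EGD specificity | 50/50 = 100% | 44/44 = 100% |

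Raw yield is 6 v 6, p = 1.0, in both columns.

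**Illustration 2: range over b.** Assumed N = 70, a = 14, c = 4, with all EGD-only findings accepted by the panel.

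| | b = 2 (d = 50) | b = 10 (d = 42) |
|---|---|---|
| EGD reference: capsule sensitivity | 14/18 = 77.8% | 14/18 = 77.8% |
| EGD reference: capsule specificity | 50/52 = 96.2% | 42/52 = 80.8% |
| EGD reference: capsule PPV | 14/16 = 87.5% | 14/24 = 58.3% |
| Panel accepts all: sensitivity, capsule v EGD | 16/20 = 80.0% v 18/20 = 90.0% | 24/28 = 85.7% v 18/28 = 64.3% |
| Panel accepts half of b: sensitivity, capsule v EGD | 15/19 = 78.9% v 18/19 = 94.7% | 19/23 = 82.6% v 18/23 = 78.3% |

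With EGD as reference, EGD is 100% in every cell.

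**Circularity under the panel.** Suppose a test is positive when the panel grades its finding D2, and the reference is positive when the same panel says a D2 finding is present. Every test-positive is then reference-positive, so false positives are zero and specificity and PPV are 100% for both tests by construction. The 100% panel specificities in Illustration 1 show exactly this. Changing the name of the reference is therefore not enough.

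**The case against.** The strongest reply is that little of the primary analysis is at risk. Section 10.5 heads it as diagnostic yield, and McNemar's test on paired D2 yield needs no reference. This stands. A reader might infer that the whole primary effectiveness result hangs on the choice; the documents do not support that. Only the four accuracy measures, and any paired test of them, are affected. The plan does not say which of these McNemar's test is meant for.

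A reader might also infer that every capsule-only lesion becomes an error. It does not: the analysis in 6.7 is per patient, so someone with a capsule-only lesion and another D2 finding on EGD is still a true positive. Only patients with no D2 finding on EGD are affected.

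Nor are the two instructions strictly exclusive. EGD-referenced capsule figures could sit beside panel-referenced figures for both tests, and three endpoint-specific texts would probably outweigh one general sentence. But the plan supplies neither a label nor an order of precedence.

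On abnormal v relevant, the paragraph in 4.2 itself targets clinically relevant pathology and counts only D2. Loose wording is the likelier explanation, and a deliberate D0/D1 reference is not the natural reading.

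The earlier studies in section 2 used EGD or gastroscopy as reference. They are background and do not settle the matter. That this is a pilot without a success criterion lowers the stakes but does not remove the contradiction.

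**Conclusion.** The contradiction is in the current text and should be resolved before the accuracy results are computed. Under 10.1, EGD's 100% on all four measures holds for any data, and so does the rule that the capsule can at best tie. The loss to the capsule relative to the panel standard arises whenever the experts accept at least one finding in a patient positive on the capsule alone.

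The size is not known from the documents. In the assumed examples, equal yields turn into a 30-point sensitivity deficit (70.0% v 100%, p = 0.031). With ten capsule-only patients all accepted, a 21.4-point capsule advantage (85.7% v 64.3%) becomes a 22.2-point deficit (77.8% v 100%). With two capsule-only patients, the capsule's own sensitivity moves only from 77.8% to 80.0%. These figures rest on invented counts and on the stated share of findings that the panel accepts. The comparison of raw D2 yield does not change. The wording difference in 4.2 is minor and needs only to be aligned.

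**What to change.** 1. In 10.1, replace EGD as the gold standard with the expert group's decision that a relevant (D2) finding is present. In 4.2, change abnormal to relevant (D2), to match the synopsis and 10.5.
2. If EGD-referenced figures are wanted for comparison with the earlier studies, report them for the capsule only, labelled as secondary agreement statistics.
3. In 6.7, state how the two independent reviews are combined into one decision, including what happens when they disagree. Writing consensus into 10.1 would not do this, because 6.7 describes no consensus step.
4. Take each test's positive or negative call from its own procedure report, made blind to the other test, and not from the panel grade. Section 6.5 already keeps the endoscopist unaware of the capsule findings and has a capsule report written for each patient. As 6.7 is the only place where D grades are assigned, the reports would need a field for the D2 call.
5. State whether McNemar's test is applied to raw D2 yield, to sensitivity and specificity, or to both.

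The cost is a few sentences in 10.1, 10.5, 4.2 and 6.7 and one field per report, with no added procedures or visits. The remaining weakness is that the panel sees both examinations when it sets the reference, so some incorporation bias persists and should be acknowledged in the report.

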Study Endpoints	
Primary
 
Effectiveness:
 
For both MCC, MCC-T and EGD, rates of diagnosis of clinically relevant pathology in patients with upper abdominal pain will be assessed. Detection of D2 findings (clinically relevant) will be considered positive. Sensitivity, specificity, positive predictive value, and negative predictive values will be calculated for both MCC or MCC-T and EGD. In this study the “gold standard” will be the expert group’s decision regarding the presence of a relevant finding. McNemar’s test will be used to assess for statistically significant differences between the two modalities. Sub-analyses will be performed to compare accuracies of the two modalities based on anatomic region (i.e. esophagus, stomach, duodenum) and across various lesions (i.e. ulcers, gastropathy, esophagitis, etc.).
 
Safety: Rate of device or procedure related adverse events during the procedures or in the follow-up period (24 hrs. post procedure).
 
Secondary
 
Examination completion: Compare rates of complete examination of the foregut by MCC, MCC-T and EGD in patients presenting with upper abdominal complaints using sets of predetermined still images
 
Patient Satisfaction: Assess patient satisfaction for patients undergoing MCC or MCC-T and EGD.

Inclusion Criteria	
 1. Patient is 18 years up to 75 years 2. Patient is able to provide informed consent

	
 3. Patient has appropriate indications for EGD including symptoms of, but not limited to upper abdominal pain, acid reflux, heartburn, iron deficiency anemia, weight loss, bloating, belching, nausea, vomiting and atypical chest pain. 4. Patients are COVID-19 negative by PCR testing 1-3 days prior to EGD or fully vaccinated against SARS-CoV-2 (at least two weeks after final dose of authorized or approved vaccine) and completion of a symptom screening questionnaire before participating in the study.

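### Section 10.1 takes EGD as the reference for the four accuracy measures, while the synopsis, 4.2 and 10.5 take the expert group's decision and also require EGD's own accuracy

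*Combined protocol and SAP*

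**What the plan says.** Section 10.1 (Statistical Methods) is unqualified: sensitivity, specificity, positive predictive value and "negative predictive value will be calculated using EGD as the gold standard".

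The primary effectiveness endpoint is written differently in three other places.

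- Synopsis, Study Endpoints: "Sensitivity, specificity, positive predictive value, and negative predictive values will be calculated for both MCC or MCC-T and EGD". The reference there is the expert group's judgement that a relevant finding is present.
- Section 4.2: the reference "will be the expert group’s decision regarding the presence of an abnormal finding".
- Section 10.5: "negative predictive values will be calculated for both MCC-T and EGD", and the reference "will be the expert group’s decision regarding the presence of a relevant finding".

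All three count a D2 finding as a positive result, and all three name McNemar's test for comparing the modalities. Section 10.1 does not mention McNemar's test.

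Section 6.7 describes the review. Two attendings look at both exams, ask whether either of them showed a lesion highly likely to explain the symptoms, and grade findings D0 to D2. No section ranks the two references or labels one as secondary. The EGD reference in section 2 belongs to the earlier studies in China and does not settle the matter for this one.

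**The concern.** The two rules produce different tables from the same patients. If EGD is the reference, its sensitivity, specificity, PPV and NPV are 100% by definition. The EGD half of the accuracy results, which three sections require, then carries no information. Section 6.7 lets the reviewers count a lesion that only the capsule showed. Under 10.1 that same lesion is a capsule false positive, so every disagreement between the exams counts against the capsule.

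At stake are the accuracy figures in the primary effectiveness endpoint. An analyst could follow either section, even after seeing the data, and claim to have followed the plan.

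**Working it through.** The plan gives no expected prevalence, accuracy target or cell counts, so there is no figure to reproduce. What follows is an illustration.

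**Inputs.** The total of 70 patients is from 10.6. The synopsis gives 100 patients plus 10 volunteers, and 5.2 gives up to 100 including up to 30 volunteers. The cell counts are assumed: *a* = 15 (D2 on both exams), *b* = 8 (capsule only), *c* = 4 (EGD only), *d* = 43 (neither). I take the expert group to be the reviewers in 6.7 and assume that they accept every D2 finding from either exam.

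**EGD as reference (10.1).**

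- Capsule sensitivity = a/(a+c) = 15/19 = 78.9%
- Capsule specificity = d/(b+d) = 43/51 = 84.3%
- Capsule PPV = a/(a+b) = 15/23 = 65.2%
- Capsule NPV = d/(c+d) = 43/47 = 91.5%
- EGD: 100% on all four by definition

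**Expert group as reference (synopsis, 4.2, 10.5).** Reference positives = a+b+c = 27; reference negatives = 43.

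| | Capsule | EGD |
|---|---|---|
| Sensitivity | 23/27 = 85.2% | 19/27 = 70.4% |
| Specificity | 43/43 = 100% | 43/43 = 100% |
| PPV | 23/23 = 100% | 19/19 = 100% |
| NPV | 43/47 = 91.5% | 43/51 = 84.3% |

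Specificity and PPV are 100% for both tests only because the panel is assumed to accept every D2 finding.

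**What does not change.** D2 detection is 23/70 = 32.9% for the capsule and 19/70 = 27.1% for EGD under either reference. McNemar's test on paired D2 positives uses only the 8 and 4 discordant patients. The exact two-sided p = 2 × (1 + 12 + 66 + 220 + 495)/4096 = 1588/4096 = 0.39. The reversed ranking in sensitivity is therefore not a statistically significant difference.

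**If the panel rejects some findings.** Take *a* = 15, *b* = 6, *c* = 4, *d* = 45, with 5 of the 6 capsule-only and 3 of the 4 EGD-only findings confirmed. Reference positives are 15 + 5 + 3 = 23 and negatives 47. Capsule sensitivity is 20/23 = 87.0% and EGD sensitivity 18/23 = 78.3%. Specificity is 46/47 = 97.9% for each. Against EGD, the same data give the capsule 15/19 = 78.9% and 45/51 = 88.2%.

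**When the two references coincide.** If the panel in that second table rejects all 6 capsule-only findings and confirms all 4 EGD-only findings, its decision equals the EGD result in every patient. Both references then give capsule sensitivity 78.9% and specificity 88.2%, and EGD 100%. The conflict has no numerical effect only under such complete agreement.

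**The case against.** Three of the four places agree. The specific efficacy section is one of them, whereas 10.1 is a general methods paragraph. This is a pilot without a success threshold or powered hypothesis, and an analyst would probably follow 10.5. That is fair as a prediction, but no rule of precedence is written down, and 10.1 names the same four measures without qualification.

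A second objection is that the panel reference is itself imperfect, and this stands. The reviewers grade D2 after seeing both exams, so a D2 positive is close to being the panel's own decision. Against that reference both tests can miss lesions, but false positives will be rare. This is a limitation to report. It does not make the two rules compatible.

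Two stronger readings are tempting, and the documents support neither.

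- A reader might infer that under 10.1 the trial could never show the capsule to equal or exceed EGD. The primary endpoint begins with rates of diagnosis, and these do not depend on the reference. In the first table the capsule leads 23 to 19 under either rule.
- A reader might infer that McNemar's test under 10.1 could only go against the capsule. McNemar's test appears only in the sections that name the expert group, so pairing it with the EGD reference creates a test that no section specifies.

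**Conclusion.** The contradiction is real and sits in current text on the primary endpoint. It is confined to sensitivity, specificity, PPV and NPV, and it changes them whenever the panel and EGD disagree in at least one patient. In the first illustration capsule sensitivity moves from 78.9% to 85.2% and EGD sensitivity from 100% to 70.4%, so the ranking reverses. All cell counts are assumed, so these figures show direction rather than expected size. The number analysed may also be below 70, because 10.2 limits the analyses to subjects who swallowed the tethered capsule while 10.6 randomises between MCC and MCC-T.

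The panel standard also has two wordings. Section 4.2 refers to the "decision regarding the presence of an abnormal finding"; the synopsis and 10.5 refer to the "decision regarding the presence of a relevant finding". An abnormality unlikely to explain the symptoms (D0) could be reference-positive under the first and not under the second. Pointing 10.1 at both sections would leave two definitions in force.

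**What to change.** 1. In 10.1, replace the EGD reference with the expert group's decision on the presence of a relevant (D2) finding, and say that the four measures are calculated against it for both the capsule and EGD.
2. In 4.2, change abnormal to relevant, so that the synopsis, 4.2, 10.1 and 10.5 carry one definition.
3. If an EGD-referenced figure is wanted for comparison with the earlier studies, report it for the capsule only, as a secondary result named positive and negative percent agreement with EGD. Do not calculate EGD's accuracy against itself.
4. State as a limitation that the panel judges from the two exams being compared, so specificity and PPV against it are expected to be close to 100%.

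The cost is one sentence in 10.1, one word in 4.2, one sentence on the limitation and, if wanted, one labelled secondary table. No new data or procedures are needed.

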10.2 Study Populations

The safety population will include all subjects who swallowed the NaviCam Capsule with tether and underwent upper endoscopy. All safety and efficacy analyses will be performed on the safety population.

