4 STUDY OBJECTIVES

4.1 Study Objectives

Primary:

1. To demonstrate the effectiveness of the MCC and MCC-T when compared to EGD in identifying esophageal, gastric and duodenal abnormalities in patients presenting with upper abdominal symptoms.
2. To evaluate rates of adverse events and overall safety of MCC-T as compared to EGD.

Secondary:

1. To compare rates of complete examination of the foregut by MCC, MCC-T and EGD in patients presenting with upper abdominal complaints using sets of predetermined still images
2. To assess patient satisfaction for patients undergoing MCC, MCC-T and EGD.

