6.5 Visit 2 – MCC, MCC-T and EGD Procedure

Upon being checked in, the subject will be brought to the study area with the NaviCam System. A study staff member (NP/Attending/Fellow) trained in the MCC-T procedure will review the study procedure with the patient and confirm that the patient has been NPO for at least 8 hours. The patient will drink about 250ml of water prior to ingesting the capsule containing 1-2 drops of simethicone (infant formulation).

Examination of Esophagus:

The sensor array jacket will be attached to the patient. After the capsule is activated the patient will swallow the capsule (attached to a tether) in the sitting position. It will then be slowly lowered down the esophagus for a complete exam. Alternatively, the patient will be placed in the prone position with a 10° elevation of the head and ingest the capsule without the tether using sips of water. The study staff member will then record the video of the examination of the esophagus by moving the capsule down the esophagus using the magnetic field.

Images to be obtained:

1. Upper esophagus

2. Middle esophagus
3. Lower esophagus
4. Z line.
5. Any pathological lesions

Examination of Stomach:

Once the examination of the esophagus is complete and the capsule is in the stomach, the tether, if used, will be used to view the stomach as the patient drinks about 500 to 1000 cc of water with 4 drop of simethicone to ensure adequate gastric distention. The tether is then detached from the capsule by injecting air through the tether causing separation of the two components. The tether is withdrawn. Then instructed to lay down per physician instructions. The study staff member will begin controlling the device using the magnetic system. The patient will move their position in a predetermined patent to enhance complete visualization of the stomach as was done in the esophagus, a video will be recorded of the full examination. Photo documentation in accordance with a gastric mapping protocol will also be done. This includes images of the following:

- Distal Antrum
- Centered view of the pylorus
- Proximal Antrum
- Two pictures along the length of the incisura
- Distal body
- Mid/proximal body (lesser curvature)
- Mid/Proximal body (greater curvature)
- Gastric fundus
- Gastric cardia
- Any gastric pathology (e.g. gastric varices, gastric ulcers, gastropathy, polyps, etc.)

Examination of duodenum:

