10.6 Sample Size

Since there is no predicate data in the United States we have elected to do a pilot study involving 70 patients and up to 30 volunteers who will help the investigators optimize the technique with the MCC and MCC-T. We will allocate patients to MCC or MCC-T randomly using a randomization protocol generated by Redcap

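### Sections 10.2 and 10.5 contradict the randomisation, objectives and endpoints on whether the untethered capsule (MCC) is analysed; read literally, MCC patients leave both primary endpoints

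*Combined protocol and SAP*

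**What the plan says.** - **Allocation (10.6):** "We will allocate patients to MCC or MCC-T randomly using a randomization protocol generated by Redcap". No ratio is stated. The size is 70 patients plus up to 30 volunteers.
- **Procedure (6.5):** after the tethered technique, the section gives as an alternative that the patient will "ingest the capsule without the tether using sips of water". It does not refer to the allocation.
- **Objective (4.1):** the first primary objective begins "To demonstrate the effectiveness of the MCC and MCC-T when compared to EGD".
- **Endpoint (synopsis and 4.2):** rates of clinically relevant diagnosis are to be assessed for MCC, MCC-T and EGD.
- **Population (10.2):** "The safety population will include all subjects who swallowed the NaviCam Capsule with tether and underwent upper endoscopy". The next sentence reads "All safety and efficacy analyses will be performed on the safety population". No other population is defined.
- **Analysis (10.5):** "For both MCC-T and EGD, we will be assessing rates of diagnosis of clinically relevant pathology". For the accuracy measures, "negative predictive values will be calculated for both MCC-T and EGD". Photo documentation, under technical success, also names only MCC-T and EGD.

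**The concern.** A patient who swallows the untethered capsule cannot meet the definition in 10.2, and that definition governs every safety and efficacy analysis. An analyst who follows the text would therefore report neither effectiveness nor adverse events for one of the two randomised devices, although the first primary objective asks about both.

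An analyst who sees the conflict has to choose among tethered only, untethered only and pooled. Each choice can be defended from some section, and it could be made after the results are known. Pooling without a split by device could also hide a difference in the esophagus, the segment that section 3.5 says the tether is there to show.

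The same sentence has a second effect. Because it also requires EGD, a patient who swallowed a capsule but never had EGD falls outside the safety set, and so do that patient's adverse events.

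**Working it through.** **Step 1. Which device each section names.**

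| Item | Synopsis | Section 4 | Section 10 |
|---|---|---|---|
| Diagnosis rate | MCC, MCC-T, EGD | MCC, MCC-T, EGD (4.2) | MCC-T, EGD (10.5) |
| Accuracy measures | MCC or MCC-T, and EGD | MCC and EGD (4.2) | MCC-T and EGD (10.5) |
| Safety objective | MCC and MCC-T | MCC-T alone (4.1) | tethered set only (10.2) |
| Completeness of examination | MCC, MCC-T, EGD | MCC, MCC-T, EGD (4.1) | MCC-T, EGD (10.5) |

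The accuracy sentence exists in three versions that name three different things. Of the places compared, only sections 10.2 and 10.5 consistently leave the untethered device out.

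**Step 2. The plan's own number.** Section 10.6 gives 70 + 30 = 100, which agrees with section 5.2 (up to 100, including up to 30 volunteers). The synopsis gives 100 + 10 = 110, which does not. No significance level, power or effect size is stated, so the number cannot be derived. N = 70 is used below.

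**Step 3. Patients left under 10.2.** The ratio is an assumption, written MCC-T to MCC.
- 1:2 gives 70 × 1/3 ≈ 23 kept, 47 lost.
- 1:1 gives 70 × 1/2 = 35 kept, 35 lost.
- 2:1 gives 70 × 2/3 ≈ 47 kept, 23 lost.

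**Step 4. Safety.** With no events in n patients, the one-sided 95% upper bound is 1 − 0.05^(1/n).
- n = 70: 4.2%
- n = 47: 6.2%
- n = 35: 8.2%
- n = 23: 12.2%

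With the synopsis figure of 100 patients and 1:1, the bounds are 1 − 0.05^(1/50) = 5.8% against 1 − 0.05^(1/100) = 3.0%.

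**Step 5. Effectiveness.** Exact (Clopper-Pearson) 95% intervals for a detection rate near 50%, an assumed value:
- 35/70: 37.8% to 62.2%, half-width 12.2 points
- 24/47: 36.1% to 65.9%, half-width 14.9 points
- 18/35: 34.0% to 68.6%, half-width 17.3 points
- 12/23: 30.6% to 73.2%, half-width 21.3 points

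Steps 3 to 5 are illustrations. They assume that every randomised patient swallows the allocated capsule and has EGD.

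**The case against.** The strongest reply is that this is leftover wording. The documents use MCC-T loosely for the capsule procedure in general: the schedule in 6.2 heads Visit 2 with MCC-T above a row labelled MCC, 6.5 speaks of MCC-T ingestion and images for what must be all patients, and 3.5 calls the tether optional. The synopsis and 4.2 still plan MCC results. On this view any sensible analyst would include both arms.

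Much of that stands as an explanation for 10.5. It is less convincing for 10.2, which specifies the tether outright. A tether-only study is also a credible reading: section 8 describes the study as evaluating the capsule with its tether, the opening of section 10 has readers compare MCC-T with endoscopy images, and the safety objective in 4.1 names MCC-T alone.

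Two further replies are correct and limit the point:
- The main comparison is capsule against EGD within the same patient, so randomisation is not its basis, and no objective compares MCC with MCC-T. A between-arm test is not missing from the plan.
- The alternative technique in 6.5 can be read as describing two methods while 10.6 decides who gets which. Operator choice is an inference, not something the text states.

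A reader might also infer that McNemar's test is misapplied because three devices are named. It is not. Each patient has one capsule type and then EGD (6.4, 10.6), so the pair has two members.

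**Conclusion.** The contradiction is real and needs correcting before analysis. Taken literally, the only defined population removes patients given untethered MCC from both primary endpoints, while the randomisation, the effectiveness objective and the endpoints include them.

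At an assumed 1:1 allocation of 70 patients the loss is 35, and it is 23 to 47 across 2:1 to 1:2. That roughly doubles the zero-event safety bound at 1:1. The ratio is not stated and the documents disagree on N, so these figures show scale only.

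Two stronger readings are not supported:
- **That the sponsor decided to drop the untethered arm.** The synopsis, 4.1 and 4.2 still promise results for it.
- **That every output excludes it.** The data listings in 10.1 and the baseline summaries in 10.3 are not expressly tied to the population in 10.2.

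The 4.2 accuracy sentence is also not evidence of a tether-only plan. It names MCC, which shows inconsistent labelling.

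**What to change.** - **10.2:** define the safety set as all subjects who swallowed either capsule (MCC or MCC-T), whether or not EGD followed. Define the paired efficacy set as subjects with either capsule and EGD.
- **4.1, 4.2 and 10.5:** name both capsules consistently, including in the safety objective of 4.1. Report capsule-versus-EGD accuracy, McNemar's test, completeness, satisfaction and adverse events for MCC, MCC-T and pooled, by randomised arm. Label the arm-level results as estimation.
- **10.6:** state the allocation ratio.
- **6.5:** reconcile the alternative technique with the random allocation in 10.6.
- **Optional:** give an MCC versus MCC-T difference with a 95% confidence interval, labelled descriptive. No current objective requires it.

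The cost is wording and a few extra tables. No additional patients or procedures are needed. Arm-level intervals will be wide, which is acceptable in a pilot if they are presented that way.
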